11.8.2 Exposure ascertainment

Information on all prior RSV vaccine doses will be collected. Vaccination status, vaccination date, vaccine dose and vaccine name and brand information are required. Depending on the Study Contributor, the source for exposure ascertainment will be different and may include vaccination registries, medical records, or vaccination cards. Information on the source documentation of the exposure ascertainment will be collected.

Patients that cannot be classified into one of the exposure categories (i.e., their vaccination status is unknown) will be excluded.

11.9 Covariates

The complete dataset can be found in the id.DRIVE common dataset case report form (eCRF) and is summarised in Table 1. All covariates are being collected for both prospective and retrospective subjects, if available.

Covariate ¹⁷	Description
Age at hospital admission	Years, calculated based on date of birth and date of admission
Gender assigned at birth	Male, female
Chronic conditions*	
Asthma	Binary
	If yes, subcategory 'Mild intermittent', 'Mild persistent',
	'Moderate persistent', 'Severe persistent', 'No information'
Lung disease	Binary
	If yes, subcategory 'COPD' and stage (GOLD I – IV, No
	information)
Cardiovascular disease	Binary
	If yes, subcategory 'Congestive heart failure'
Hypertension	Binary
Chronic liver disease	Binary
	If yes, subcategory 'End-stage liver disease (ESLD)': 'No', 'Yes',
	'No information'
Chronic renal disease	Binary
	If yes, subcategory 'End-stage kidney disease (ESKD)': 'No', 'Yes
	but without dialysis', 'Yes and on dialysis', 'No information'
Diabetes type I	Binary
Diabetes type II	Binary
Obesity	Binary
Cancer	Binary
	If yes, specification of subcategories: 'Solid tumour',
	'Haematological cancer', 'No information'.
	If solid tumour or haematological cancer is yes, further
	specification of cancer type to be selected from list.

Table 1. Study covariates and health care use

¹⁷ Some covariates might not be collected across all Study Contributors. This will be specified in the Study Requestor-specific protocol and SAP after completion of feasibility assessments.

Covariate ¹⁷	Description
Immunodeficiency (or	Binary
organ transplant)	If yes, specification of subcategories: 'Solid organ or islets
	transplant', 'Hematopoietic stem cell transplantation', 'Primary
	immunodeficiency', 'Advanced or untreated human
	immunodeficiency virus (HIV) infection', 'latrogenic
	immunodeficiency', 'Other'. If solid organ or islets transplant is
	yes, specification of subcategories: 'Kidney', 'Liver', 'Intestines',
	'Heart', 'Lung', 'Pancreas', 'Other', 'No information'
Neurological disorders	Binary
Receiving chronic oxygen	Binary (defined as oxygen used for at least 15 h per day in
supplemental therapy	chronically hypoxaemic patients)
Body mass index (BMI)	Continuous
Smoking history	Never smoker, ex-smoker, occasional smoker, daily smoker, no
0 1	information
Vaccination history RSV	Binary
	If yes, was it investigational RSV vaccine, brand, date, and source
	of information
Vaccination history COVID-19	Binary
	If yes, brand, date, and source of information
Vaccination history influenza	Binary, within 12 months prior to the modified SARI hospital
	admission
	If yes, brand, date, and source of information
Vaccination history	Binary, at least one vaccination in the past
pneumococcus	If yes, brand, date, and source of information
Long-term care facility	Binary, if no, specification of residential situation before
residence	hospitalisation: 'Home', 'Home with nursing care', 'Transfer from
residence	another hospital', 'Rehabilitation centre', 'Nursing home',
	'Other', 'No information'
History of RSV in the current	Binary
season before symptom onset	If yes, date.
leading to this hospitalisation	n yes, date.
Prior modified SARI	Binary,
hospitalisation episode in	If yes, time since most recent prior modified SARI hospitalisation
previous 12 months	n yes, time since most recent phot mounied shar hospitalisation
Month and year of prior SARI	Month and year
episode	
Respiratory support	'None', 'Oxygen therapy', 'Non-invasive ventilation', 'Invasive
	mechanical ventilation', 'Extracorporeal membrane oxygenation
	(ECMO)', 'No information'
ICU admission	Binary, date of admission, date of discharge
In-hospital death	Binary, date of hospital discharge or in-hospital death
Post-discharge destination	'Home', 'Home with nursing care', 'Transfer to another hospital',
	'Rehabilitation centre', 'Nursing home or other long-term care
	facility', 'Other', 'No information'
Length of hospital stay	Days, continuous
Treatments received during	'Antibiotics', 'Antiviral drug(s)', 'Corticosteroid(s)', 'Immune
hospital stay for the	modulator(s)', 'Anti-RSV antibodies', 'Other monoclonal
management of modified	antibodies', 'None of the above'.
-	
SARI episode	Brand name, if anti-RSV antibodies received during hospital stay

Covariate ¹⁷	Description
Treatments received prior to	'Antibiotics', 'Antiviral drug(s)', 'Corticosteroid(s)', 'Anti-RSV
hospital admission for the	antibodies', 'Other monoclonal antibodies', 'None of the above'.
management of current	Brand name, if anti-RSV (or other monoclonal) antibodies
modified SARI episode	received during hospital stay
Medicinal product for the	Binary
prevention of RSV infection	If yes, type ('Antiviral drug', 'Anti-RSV-antibodies', 'Other'),
within 12 months prior to	brand and date (month/year) if anti-RSV-monoclonal antibody
current hospitalisation	
Laboratory results (RSV)	Type of specimen(s), date(s), RSV subtype(s)
Laboratory results (SARS-CoV-	Type of specimen(s), date(s), genetic variant(s)
2)	
Laboratory results (Influenza)	Type of specimen(s), date(s), subtype(s)
Laboratory results	Type of specimen(s), date(s), identified pathogen(s), subtype(s)
(other pathogens)	and genotype(s) [if applicable]

* Definitions for each chronic condition are specified in the id.DRIVE Common dataset case report form. Abbreviations: COPD, chronic obstructive pulmonary disease; COVID-19, coronavirus disease 2019; ECMO, extracorporeal membrane oxygenation; ESLD, end-stage liver disease; ESKD, end-stage kidney disease; GOLD, Global Initiative for Chronic Obstructive Lung Disease; ICU, intensive care unit; RSV, respiratory syncytial virus; SARI, severe acute respiratory infection; SARS-COV-2, severe acute respiratory syndrome coronavirus 2

11.10 Sample size considerations

The technical considerations for the calculation of the targeted samples sizes are detailed in Annex 1. The sample size requirements strongly depend on the objectives (primary vaccination, seasonal vaccination), on case-control ratio, overall vaccination coverage and share of the different vaccine brands. Due to the nature of the TNCC design, all cases and controls are recruited and data on them are collected. This is a key aspect of the TNCC design and additionally crucial for surveillance use-cases. If balancing of case-control ratios is desired, these can be handled at the analysis stage for brand-specific analyses. As such, the sample size requirements and assumptions will be different for each vaccine brand and defined by the Study Team. Sample size requirements will be calculated for each Study Requestor-specific protocol (for both interim and final analysis when applicable). In case the parameter settings used for these sample size calculations are very different from what is observed in the study, the sample size calculations will be updated accordingly with the progress reports.

11.11 Data management

Data collection, statistical analysis and preparation of the study report are activities firewalled from vaccine companies to avoid perception of undue influence on the study report and VE results interpretation.

11.11.1 Data management at Study Contributor level

Each Study Contributor is responsible for the data collection and data management of their participant-level study data. Depending on the Study Contributor, the data collection and source

documentation will be different. A Source Data Location Form for variables is collected during a site initiation visit (SIV).

11.11.2 Data flow

- 1. The Study Contributor collects the data and enters/uploads it in the Castor[®] electronic data capture (EDC) system.
- 2. The Study Sponsor validates the data, raises applicable queries and the Study Contributor responds to data queries by updating or confirming the data.
- 3. The Study Sponsor imports the data from all participating Study Contributors in a secure environment using the EDC system's export functionality.
- 4. The Study Sponsor transforms all data to generate the output as pre-specified in the SAP within the secure environment.

P95 reviews the imported variables on a bi-weekly basis. These data review checks are detailed in a Data Validation Plan.

A DMP is written prior to the start of the data collection to describe data management at the central level. The DMP describes all functions, processes, responsibilities and specifications for data collection, data storage, quality checking, transfer, cleaning, and validation. The DMP is updated regularly. All statistical analyses will be conducted in the id.DRIVE research server.

11.12 Data analysis

An SAP will be developed prior to the conduct of the analysis. The SAP specifies all statistical analyses, including sensitivity analyses, to be conducted, and will include tables shells and mock figures.

11.12.1 Context information

Context information will be provided in study reports by describing the circulating RSV subtypes during the study period in the countries (or regions) where the Study Contributors are located. National (or regional) RSV vaccination recommendations over time will be described (including licensed age groups, contraindications, number of doses and timing between doses). The external data sources used to describe the RSV viral distribution, vaccination coverage, and vaccination recommendations will be specified in the SAP.

11.12.2 Attrition diagram

The study report(s) will include an attrition diagram. The attrition diagram describes the number of records excluded from the statistical analyses, by reason of exclusion.

11.12.3 Descriptive analysis of demographics and baseline characteristics

Visualisations based on the final vaccine brand/product-specific data for analysis will be created including:

- number of test-negative controls and test-positive cases (possibly by RSV subtypes) over time
- distribution of covariates among controls and cases

A tabular summary based on the final brand/product-specific data for analysis will be created, describing the characteristics of cases and controls as predefined in the SAP.

11.12.4 Statistical analyses

VE is defined as $(1 - OR) \times 100\%$, where *OR* denotes the (exposure) odds ratio, comparing the confounder-adjusted odds of vaccination among RSV-positive study participants to the odds of vaccination among RSV-negative study participants.

VE estimates will be adjusted for calendar time at minimum, and additionally the following confounders – age, sex, and comorbidities (e.g. number of chronic conditions). Adjustments are usually achieved through inclusion of the relevant terms in the logistic regression models, with (penalised) spline terms for calendar time and age. However, other methods may be considered as well.

Clusters will be defined at the hospital network (Study Contributor) level. If some networks have hospitals that are very different (e.g. geographically separated), then clustering could be defined at the hospital level for these networks. However, similarities between these hospitals may remain due to being part of the same hospital network, in which cases these would not be treated as being independent of each other.

An important choice is whether the exposure odds ratios are desired to have a subject-specific (SS) or population-averaged (PA) interpretation [16]. The SS OR compares odds of vaccination among the RSV-positive cases to the odds of vaccination among the RSV-negative controls from the same Study Contributor (conditional on other covariates) and necessitates the inclusion of a fixed-effect or a random-effect term for Study Contributor in a multivariable model, or via a meta-analysis. The PA OR compares the odds of vaccination among the RSV-positive cases across the Study Contributors to the odds of vaccination among the RSV-positive cases across the Study Contributors to the odds of vaccination among RSV-negative controls across the Study Contributors (conditional on other covariates) and is commonly obtained from a GEE model. Care should be taken with regards to method selection (estimators for point-estimates and standard errors) to avoid biased VE estimates when the clustering variable is a potential confounder or when the cluster size is informative. For population-averaged estimates, GEE with a working independence correlation structure (IEE, or independence estimating equations) and cluster robust standard errors (Liang-Zeger) should be used. For subject-specific estimates, using a fixed-effect term for Study Contributor in a multivariable logistic regression model (GAM) is recommended due to its ease of implementation; no further adjustments to the standard errors are required.

If effect modification / treatment effect heterogeneity by Study Contributor is of interest, a stratified analysis by Study Contributor can be carried out. Alternately, Study Contributor-specific VE estimates can be obtained by adding interaction terms between Study Contributor and exposure in the models.

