- the effect of redefining the positive case group, by including only RSV tested-positive cases without a coinfection, and
- the effect of patients having ≥ 2 laboratory-confirmed RSV infections in the current season.

All sensitivity analyses will be pre-specified in the SAP.

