13 LIMITATIONS OF THE RESEARCH METHODS

- Due to high demand and limited vaccine supplies, European countries often prioritise highrisk groups such as the elderly, residents in care facilities, and those with specific chronic conditions. This prioritisation creates potential confounding factors in studies on VE. Untangling waning of vaccine-induced immunity, varying VE against different RSV subtypes, and infection-acquired immunity is challenging due to the complex interaction of these factors.
- Infection-acquired immunity protects against re-infection but may wane and act as an effect modifier of VE. Hybrid immunity, combining infection-acquired and vaccine-induced immunity, is suggested for optimal protection against severe disease. However, identifying past RSV infection poses challenges due to potential underreporting or misclassification, especially with clinical-based diagnoses and the absence of serological results. This prior infection status could also introduce confounding, influencing vaccination decisions.
- The TNCC study design minimises unmeasured confounding tied to general health careseeking behaviour [24]. However, specific health practices may still confound results. Vaccination uptake may be higher among individuals strongly adhering to preventive practices such as social distancing, reducing natural infection risk. Conversely, being vaccinated may lead to a false sense of security, relaxing precautions and increasing exposure risk. Additionally, those likely to get vaccinated against RSV may also favour influenza, SARS-CoV-2, and/or pneumococcal vaccinations, potentially biasing results. Sensitivity analyses redefining control groups will explore this bias. In this study, exposure ascertainment is based on multiple sources including vaccine registries, vaccination cards and medical records. Although vaccination status captured in medical records is neither validated against primary records nor validated verbally with the patient, misclassification was likely limited: complete exposure data was required for a participant to be retained in the id.DRIVE study (mandatory variables included date of administration, dose number and vaccine brand).

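### The stated adjustment set leaves out long-term care residence, which the protocol treats as a potential confounder and collects, and Table 1's coding of that item conflicts with its own discharge item

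*Protocol*

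**What the plan says.** **Adjustment set.** Section 11.12.4, repeated in the abstract, states: "VE estimates will be adjusted for calendar time at minimum, and additionally the following confounders". The list is "age, sex, and comorbidities (e.g. number of chronic conditions"). The flexibility sentence that ends the paragraph, "However, other methods may be considered as well", follows a description of regression with spline terms. It concerns how to adjust, not which covariates to use.

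**Residence.** Among the groups that countries prioritise for vaccination, section 13 names "residents in care facilities, and those with specific chronic conditions. This prioritisation creates potential confounding factors". Later in that section, long-term care residence is one of the variables collected in place of a direct frailty measure. The abstract's covariate paragraph includes it among potential confounders and/or effect modifiers.

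**Coding.** The Table 1 entry for long-term care residence reads "Binary, if no, specification of residential situation before" hospitalisation, and one of the answers listed under no is *Nursing home*. The entry for discharge destination has the answer "Nursing home or other long-term care" facility.

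**Other vaccinations.** Section 13 says that people who take RSV vaccine may also favour influenza, SARS-CoV-2 and pneumococcal vaccines, and that this could bias results. Its stated remedy is: "Sensitivity analyses redefining control groups will explore this bias". In 11.12.4.2, the item that regroups participants is "the effect of redefining the positive case group, by including only RSV tested-positive cases without a coinfection". The only control exclusion mentioned there concerns patients positive on a rapid antigen test before admission.

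**The concern.** Section 13 names three examples of prioritised groups: the elderly, care-facility residents and people with specific chronic conditions. The stated model covers the first and third but not the second. A frailty proxy that does not enter the model cannot reduce confounding by frailty. If residents are vaccinated more often, and their SARI admissions are more or less often due to RSV than those of other patients, the VE estimate is shifted even though the variable is in the database.

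The coding conflict matters once the variable is used. If nursing-home residents are entered as no, adjusting for the recorded item removes only part of the confounding.

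The missing control-group analysis concerns a separate bias. Controls may be positive for influenza or SARS-CoV-2. If RSV vaccinees are also better protected against those viruses, they are under-represented among such controls, and VE is pulled downwards.

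This is a master protocol from which the requestor- and site-specific protocols are developed, so all three points would be carried forward.

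**Working it through.** The protocol gives no figure on this point, so there is none to reproduce. The text comparison is set out above. The arithmetic below only illustrates size, and **every input is an assumption**.

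**1. Residence omitted**

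Let *p* be the share of controls living in long-term care, *c1* and *c0* the RSV vaccine coverage in residents and in others, *θ* the odds ratio of residence for RSV versus other SARI, and OR = 1 − VE. Relative expected counts:

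- Controls, vaccinated: (1−p)c0 + p·c1
- Controls, unvaccinated: (1−p)(1−c0) + p(1−c1)
- Cases, vaccinated: OR × [(1−p)c0 + p·c1·θ]
- Cases, unvaccinated: (1−p)(1−c0) + p(1−c1)θ

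Take true VE 70% (OR 0.30), p = 0.20, c1 = 0.60, c0 = 0.15. The control odds of vaccination are 0.24/0.76 = 0.3158.

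| θ | Case odds of vaccination | Observed OR | Estimated VE |
|---|---|---|---|
| 2 | 0.108/0.840 = 0.1286 | 0.407 | 59.3% |
| 1 | 0.072/0.760 = 0.0947 | 0.300 | 70.0% |
| 0.67 | 0.0601/0.7336 = 0.0820 | 0.260 | 74.0% |

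These are the extremes of the grid p = 10–20%, c1 = 50–60%, c0 = 15–20%, θ = 0.67–2. On the same grid a true VE of 0% becomes −35.7% to +13.5%.

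The result depends heavily on θ. With c0 = 15%, the same p and c1, and θ between 0.8 and 1.25, a true 70% becomes 67.1% to 72.4%. A different grid (p = 5–20%, coverage 20–40% versus 5–10%, θ = 0.5–2) gives 56.0% to 78.5%.

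**2. Residence included but miscoded**

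Take p = 10%, coverage 40% versus 10%, half of residents coded no, and a Mantel-Haenszel odds ratio adjusted on the coded item. True VE is 70%.

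| θ | No adjustment | Adjusted on miscoded item | Adjusted on correct item |
|---|---|---|---|
| 0.5 | 73.7% | 72.1% | 70.0% |
| 2 | 63.3% | 66.4% | 70.0% |

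The bias that remains is 2.1 of 3.7 points and 3.6 of 6.7 points, a little over half in each case.

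**3. Correlated vaccination**

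Let *s* be the share of control illness that influenza and SARS-CoV-2 would cause without vaccination, *e* the VE against them, and *q1* and *q0* the uptake of those vaccines in RSV-vaccinated and RSV-unvaccinated people. Then

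OR observed = OR true × (1 − s·e·q0)/(1 − s·e·q1).

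With s = 0.30, e = 0.50, q1 = 0.90, q0 = 0.50: 0.30 × 0.925/0.865 = 0.321, so a true 70% is estimated as 67.9%. For s = 30–50%, e = 40–50%, q1 = 85–95% and q0 = 40–55%, the estimate runs from 64.6% to 68.8%, a loss of about 1 to 5 points.

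**The case against.** **The list may not be final.** This is a template. Section 11.12 leaves the full specification to an SAP, which was not available for this review. Footnote 17 to Table 1 says that some covariates may not be collected at every site, with details settled after feasibility assessment. This stands: the omission is not shown to be the final model. Even so, the protocol does name a set, that set fits poorly with its own account of confounding, and the flexibility sentence does not extend to covariates.

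**A reader might infer that confounding is known to remain in the primary estimate.** The documents do not support that. They give no association between residence and RSV among SARI patients. The ranges above also ignore the planned adjustment for age, comorbidities and calendar time, which may absorb part of any effect.

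**A reader might infer that the other vaccinations also belong in the primary model.** Section 13 says only that they may bias results, and it assigns them to a sensitivity analysis. Moving them into the primary model would be a preference, not a correction.

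**A reader might see 11.12.4.2 as contradicting section 13.** Its list is expressly of analyses that can be conducted, and all are to be pre-specified in the SAP. The control-group analysis is promised but not itemised. That is a gap in the list, not a contradiction.

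**A reader might conclude that most care-home residents are miscoded.** This is not shown. Sites can still answer yes for a nursing-home resident, Table 1 only summarises the eCRF, and the sub-answer makes the error recoverable. The item is not in the stated model, so the coding affects no primary estimate today. The conflict between the two rows is nevertheless plain.

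**Cost.** The primary analysis is complete-case, so adding an item that a site does not collect could remove that whole site. This objection is sound and shapes the fix.

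**Conclusion.** The point holds in a limited form. Long-term care residence should be in the named adjustment set, because the protocol itself treats it as a potential confounder and a frailty proxy and already collects it. The two Table 1 rows disagree about whether a nursing home is long-term care and need to be reconciled. The control-group analysis that section 13 promises should be listed.

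The size and direction of the residence bias cannot be derived from the protocol. It is zero at a residence odds ratio of 1. Under the first assumed grid, without other adjustment, a true VE of 70% could be estimated at about 59% to 74%. The bias from correlated vaccination is smaller, about 1 to 5 points downwards at a true VE of 70%, again on assumed inputs and for the control-depletion mechanism alone. These are worthwhile improvements; nothing here shows that the primary estimate would be invalid.

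**What to change.** 1. **Section 11.12.4 and the abstract:** add long-term care residence to the primary adjustment set where it is collected. State a missing-data rule that keeps sites lacking it. Within collecting sites, the multiple imputation that 11.12.4.1 already foresees can be used. In a model with a fixed effect for Study Contributor, a site that never collects the item can be given a constant value and stay in, adjusted for the remaining covariates. The cost is one model term and some missing data; any residence confounding stays in place at sites without the item.
2. **Table 1 and eCRF:** remove *Nursing home* from the answers under no, or derive residence as yes when it is selected. The derivation also repairs records already entered.
3. **Section 11.12.4.2:** list the control-group analysis promised in section 13, excluding influenza- and SARS-CoV-2-positive controls. Section 11.5.1 already requires RT-PCR for both viruses, so no new data are needed. Add, as a sensitivity analysis and not in the primary model, adjustment for influenza and COVID-19 vaccination, both of which are in Table 1. The cost is two extra analyses; the first has fewer controls and so wider intervals.

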11.2 Study Contributors

In this study, the term 'Study Contributor' is used in lieu of 'study site'.

The participating Study Contributors are either individual hospitals or hospital networks. The data collection will be a prospective data collection from primary data sources (e.g., specific laboratory results) and secondary data sources (e.g., existing hospital databases, vaccine registries and linked data). Retrospective data collection will be considered to allow capture of whole epidemiological year data in Study Contributors with late set-up.

¹⁰ The list of countries will be extended as the id.DRIVE network grows.

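### The recommended fixed effect is for the Study Contributor, so where a Contributor is a network of differing hospitals, residual confounding can remain in the subject-specific VE

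*Protocol*

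**What the plan says.** Protocol section 11.2: "The participating Study Contributors are either individual hospitals or hospital networks".

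Protocol section 11.12.4 makes three statements about the cluster unit:

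- The default: "Clusters will be defined at the hospital network (Study Contributor) level".
- An option: "If some networks have hospitals that are very different (e.g. geographically separated), then clustering could be defined at the hospital level for these networks".
- A qualification: where hospitals still resemble each other because they share a network, "in which cases these would not be treated as being independent of each other".

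The same section then turns to models. It warns that the choice of method must avoid bias when the clustering variable may itself be a confounder. For population-averaged estimates it asks for independence estimating equations with cluster-robust standard errors. For subject-specific estimates, "using a fixed-effect term for Study Contributor in a multivariable logistic regression model (GAM) is recommended due to its ease of implementation", and "no further adjustments to the standard errors are required". The adjustment set is calendar time, age, sex and comorbidities; hospital is not in it. The GLM/GAM procedure in Annex 1 likewise takes Study Contributors as the fixed effects.

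**The concern.** A site variable has two jobs in this analysis. As an intercept it removes confounding by place: vaccinated and unvaccinated patients are compared within the same catchment, with the same coverage and the same RSV activity. As a cluster it tells the variance estimator which patients are correlated. The two jobs can call for different units, and the protocol does not say so. The hospital-level option is worded for clustering and is not carried into the recommended fixed-effect model.

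Read as written, a multi-hospital Contributor gets one intercept, and cases from one hospital are compared with controls from another. If those hospitals differ in both coverage and positivity, the VE is shifted. The shift can go either way, does not shrink with sample size and is not reflected in the confidence interval. Since this is the master template for brand-specific protocols, the coarser adjustment would be passed on to each of them.

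**Working it through.** The protocol gives no figure to reproduce on this point. All inputs below are assumptions, chosen to show the mechanism and its range.

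**Set-up.** One network has two hospitals with 1,000 patients each. The true OR is 0.3 (VE 70%) in both, with no other covariates. Coverage among controls is c and RSV positivity is π. In each hospital:

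- cases = 1,000π and controls = 1,000(1 − π);
- proportion vaccinated among cases: p = o/(1 + o), where o = 0.3 × c/(1 − c).

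With a single network intercept and no other covariates, the model's OR is that of the pooled 2×2 table.

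**Moderate differences: coverage 15% and 25%, positivity 6% and 10%.**

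| | Vaccinated cases | Unvaccinated cases | Vaccinated controls | Unvaccinated controls |
|---|---|---|---|---|
| Hospital 1 (p = 0.0503) | 3.017 | 56.983 | 141 | 799 |
| Hospital 2 (p = 0.0909) | 9.091 | 90.909 | 225 | 675 |
| Pooled | 12.108 | 147.892 | 366 | 1,474 |

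- Network intercept: OR = (12.108 × 1,474)/(147.892 × 366) = 0.330, VE 67.0%.
- Within each hospital the OR is 0.300, so hospital intercepts return VE 70.0%.
- Positivities exchanged: OR = (10.482 × 1,470)/(149.518 × 370) = 0.279, VE 72.1%.

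**Other settings, same formulae, true VE 70%.** In the fourth column the two positivities are exchanged between the hospitals.

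| Coverage | Positivity | VE, network intercept | VE, positivities exchanged |
|---|---|---|---|
| 20% / 20% | 5% / 15% | 70.0% | 70.0% |
| 15% / 25% | 8% / 8% | 69.6% | – |
| 10% / 30% | 8% / 8% | 68.5% | – |
| 25% / 15% | 8% / 12% | 71.7% | 67.5% |
| 30% / 10% | 8% / 12% | 72.6% | 64.1% |
| 10% / 30% | 5% / 15% | 57.3% | 78.5% |

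With a true VE of 0, the 30%/10% row gives 13.4% and −14.4%, and the 25%/15% row gives 6.8% for the first pairing.

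**Reading the table.** With equal coverage there is no shift. With equal positivity, hospital is unrelated to case status. The small attenuation that remains is non-collapsibility of the odds ratio and vanishes when the true VE is 0. Confounding needs both to differ.

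**Dilution by single-hospital Contributors.** With two 2-hospital networks plus two single hospitals (500 patients per hospital), the network-intercept VE is 68.0% or 71.4% for coverage 15%/25% with positivity 6%/10% and its exchange. It is 61.1% or 76.2% for 10%/30% with 5%/15% and its exchange. Hospital intercepts give 70.0% each time.

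**Precision cost (simulation, 300 runs, 200 patients per hospital, OR 0.3).** SD is the within-network spread between hospitals on the logit scale, with coverage and positivity uncorrelated.

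| SD | SE, network intercepts | SE, hospital intercepts | Ratio |
|---|---|---|---|
| 0 | 0.193 | 0.193 | 1.000 |
| 0.5 | 0.179 | 0.182 | 1.017 |
| 0.8 | 0.166 | 0.172 | 1.036 |

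At SD 0.8, coverage of the 95% CI was 0.897 with network and 0.950 with hospital intercepts. At SD 0.5 network intercepts did little harm (0.947). A further simulation with 50 patients per hospital also put the extra SE at about 1–2%.

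**The case against.** The strongest reply is that the protocol already foresees the harmful case. Section 11.12.4 permits hospital-level units where hospitals differ greatly, warns about confounding by the cluster, words the fixed effect as a recommendation and allows other methods. Details may be settled in the SAP once the Contributors are known. Some may be single hospitals, for which the point disappears. Part of any between-hospital difference may also be removed by adjusting for calendar time, age, sex and comorbidities, which the calculations above omit. At a true VE of 70%, moderate differences shift the log OR by at most ln(0.330/0.300) ≈ 0.095, about half of a standard error of 0.193.

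Most of this stands, and it limits the point to an improvement. What it does not answer is that the hospital option is discretionary, has no criterion beyond a general description, and concerns clustering, while the recommended model names the Contributor alone.

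Two stronger readings are tempting and are not supported:

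- A reader might infer that the protocol offers hospital-level units and then withdraws them for hospitals sharing a network. The qualifying sentence speaks only of independence. It cancels no hospital-level unit, prescribes no network intercept, and is compatible with hospital intercepts plus a network-level allowance for correlation.
- A reader might infer that the subject-specific VE will be biased. The documents give no coverage, positivity or number of hospitals per network, so only the possibility is shown.

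**Conclusion.** The point holds as a cheap improvement. By default the recommended subject-specific model adjusts for place at the Contributor level, which is coarser than necessary when a Contributor is a network. Residual confounding can then remain if its hospitals differ in both coverage and RSV positivity after the planned adjustment.

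The size cannot be known from the documents. Under assumed moderate differences a true VE of 70% moves by about 2–4 points in either direction; under large ones it ranged from 57.3% to 78.5%. These figures rest on two equal hospitals, a common OR and no other covariates. They overstate the effect in a study where many Contributors are single hospitals.

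**What to change.** In section 11.12.4, separate the two roles:

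- **Intercepts.** For multi-hospital Contributors, the subject-specific model uses a fixed effect for hospital, or conditional logistic regression stratified by hospital. Hospitals too sparse to contribute are pooled under a rule stated in advance.
- **Dependence.** The network stays the unit wherever a cluster-robust variance is used, as in the GEE. Say explicitly that the non-independence sentence concerns the variance and does not determine the intercepts.
- **Data.** Keep hospital identity alongside Contributor in the analysis dataset. The existing hospital-level option already presupposes it.

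The cost is a few sentences of protocol text and, under the assumed settings, a standard error about 1–4% larger (no increase when hospitals are alike). Hospitals without cases or without vaccinated patients will add little information. The pooling rule needs a threshold, which the documents do not supply and the study team would have to set.
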